1.3.1.4. Dosing

CT38s solution will be delivered by continuous SC infusion, via a CME T34™ programmable syringe pump), at a fixed concentration, with patient-specific dose volumes calculated to achieve the intended dose levels, specified in terms of µg/kg of body weight, or µg/kg/hour (Table 6.1).

Dose	Total Dose (µg/kg)	Priming Bolus (µg/kg)	Infusion Rate (µg/kg/h) / Duration (h)			Estimated* C _{max} (ng/ml)	Estimated* AUC (ng.h/ml)	Comment
			Initial	Escalation 1	Escalation 2			
Low	0.80	0.00	0.20 / 0:45	0.22 / 0:45	0.24 / 2:00	[proprietary data redacted]	Complete	
D1	0.11	0.00	0.03 / 0:45	0.03 / 0:45	0.03 / 2:00		No priming, no escalation	
D2	0.35	0.00	0.10 / 0:45	0.10 / 0:45	0.10 / 2:00		No priming, no escalation	

C_{max} = maximum plasma concentration, at the end of dosing; *AUC* = total area under the plasma concentration-time curve.
 * Estimated based on modeling the Phase 1 trial, in which CT38s was administered by SC bolus only and the first 2 patients dosed under this trial by SC infusion

1.3.1.4.1. CT38s Concentration

The prior Phase 1 study... [proprietary data redacted].

1.3.1.4.2. Dose Levels

Patients will be enrolled sequentially to receive either D1 or D2 doses, with at least 3 patients per dose group, and the remainder allocated determined by the tolerability to D1 and D2. In each case, the total dose will be delivered in the form of an SC infusion at a constant rate of infusion maintained for a period of 3.5 hours (~2 half-lives). This infusion dose will take place at Visit 3 (Day 29), Visit 4 (Day 31) and Visit4b, i.e., a total dose delivered over 10.5 hours.

Dosing will take place sequentially with all D1 testing taking place before D2 testing. Barring any clinically meaningful concerns with the D1 arm, including PK assessments, the D2 arm is intended to achieve higher concentrations and exposures (Table 6.1).

1.3.1.5. Dose Justification

Safety and toxicology testing of CT38 in animals [IB, Section 4] and humans [IB, Section 5], showed that the principal AEs resulting from CRF₂ stimulation were increased HR, decreased BP and decreased temperature. In animals, these effects generally correlated with ... [proprietary data redacted].

In rats, cardiovascular adjustments during stress are known to involve both CRF₁ and CRF₂ in the BNST (in the limbic system) [Oliveira 2015], while stress-induced changes in body temperature are known to occur in the hypothalamus [Vinkers 2010]. Thus, these data collectively suggest that infusions of CT38 can bring about some level of CRF₂ endocytosis within the limbic system [IB, Section 4.1.1.4]. The data further suggest that CRF₂ endocytosis... [proprietary data redacted].

The first 5 ME/CFS patients dosed under this protocol (see 6.1.2.6.), confirmed that the AEs were indeed hemodynamic, and that these occurred at substantially lower plasma concentrations than in healthy subjects (Phase 1). This apparent sensitivity of ME/CFS patients suggests that these curves may be left-shifted, and thus the amended doses seek to reduce the rate of CRF₂ stimulation.

1.3.1.5.1. Low Dose

The Low dose group (2 patients) received total doses of between 0.79 and 0.83 µg/kg at each Visit. Although this was below the MTD_b determined in Phase 1, it was associated with clinically significant hemodynamic AEs, and will not be tested further.

1.3.1.5.2. D1 Dose

The D1 dose group will receive a total dose of 0.11 µg/kg utilizing a constant infusion rate of 0.03 µg/kg/hour, repeated on each of 3 treatment days. Patients will be monitored for an additional 90 minutes (or more, as needed) after the end of infusion, before leaving the clinic.

The first 3 patients receiving the D1 dose on each of 2 separate treatment days reached maximum plasma concentrations of... [proprietary data redacted], with no evidence of carryover from the first treatment day to the second. The plasma concentrations remain below the level where hemodynamic changes were evident in the first 2 ME/CFS patients dosed... [proprietary data redacted].

1.3.1.5.3. D2 Dose

Escalation to the D2 dose group will take place provided safety and tolerability parameters for the D1 dose group support the escalation. The D2 dose group will receive a total dose of 0.35 µg/kg and utilize a constant infusion rate of 0.10 µg/kg/hour. This is projected to reach maximum plasma concentrations of... [proprietary data redacted]. Patients will be monitored for an additional 90 minutes (or more, as needed) after the end of infusion, before leaving the clinic.

It is anticipated that the revised D1 and D2 doses will be sufficient to characterize the safety, tolerability and dose-concentration relationship in ME/CFS patients. However, it might be necessary to add an additional dose, longer dosing timeframes and/or up to an additional 2 days of dosing. This will only be done following a comprehensive assessment of safety, tolerability, pharmacokinetics and efficacy.

1.3.1.5.4. Total Exposure

Long-term efficacy studies in various animal models of muscle wasting, dosed CT38 by continuous SC infusion (utilizing implanted osmotic minipumps) at doses of 100 µg/kg/day of body weight for up to 3 months in rats (5 months in hamsters). In rats, this achieved... [proprietary data redacted], with the tested animals displaying no obvious safety concerns and exhibiting robust muscle preservation. The D2 dosing paradigm is not projected to exceed total exposure of... [proprietary data redacted] ...in humans per infusion, which is several orders of magnitude below those utilized in long-term animal efficacy studies.

1.3.1.6. Dose Discontinuation

It is impossible to know the extent of any potential CRF₂ up-regulation and the related left-shift of the hemodynamic dose-response curve in ME/CFS patients. While the revised dosing paradigm is not expected to cause clinically important changes in HR or BP, these will be carefully monitored during the procedure. Baseline HR and BP measures will be made in duplicate just prior to the infusion and represent Time Zero (See Section 6.3.3.2.5). The baseline HR and BP (systolic and diastolic) will consist of the average of the duplicate readings taken in the semi-recumbent position. Dosing should be stopped in a given patient if any of the following are noted: (i) a systolic BP ≤ 90 mmHg or a ≥ 20 mmHg decrease from baseline on 3 consecutive readings; (ii) a diastolic BP ≤ 50 mmHg or a decrease ≥ 15 mmHg from baseline on 3 consecutive readings; or (iii) a resting HR ≥ 120 BPM or ≤ 45 BPM. If a patient's baseline HR or BP meet the 'stopping criteria' at baseline, the infusion must not be administered. The investigator should discuss with the medical monitor whether to bring the patient back for reassessment for study drug infusion. The time window for reassessment should not be greater than 14 days. If, after reassessment, the patient does not receive the Visit 3 infusion, then the patient should be discontinued from the study.

Lack of tolerability will be monitored in an individual patient by a careful review of the type, severity and frequency of toxicities, e.g., as described in the National Cancer Institute, Cancer Therapy Evaluation Program, Common Terminology Criteria for Adverse Events v3.0, 12Dec2003. Furthermore, a decrease

from baseline in either systolic BP of ≥ 20 mmHg or diastolic BP of ≥ 15 mmHg, on 2 readings 30 minutes apart will be reviewed for clinical manifestations of lack of tolerability.

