1.3.2.2. Exclusion Criteria

A patient who meets any of the following criteria will be excluded from participation in this study:

- Alternate medical or psychiatric illness that could explain the ME/CFS symptoms
- Active or uncontrolled co-morbidities which in the opinion of the PI may interfere with the ability of the patient to participate in the study. Co-morbidities may include acute infection, Crohn's disease, diabetes mellitus (Type 1 or Type 2, evidenced by a history of hemoglobin A1C > 7 at any time), Guillain-Barre syndrome, lupus, multiple sclerosis, myasthenia gravis, rheumatoid arthritis, or other such diseases that may be exclusionary. Particularly conditions or medications that cause immunodeficiency or immunosuppression will be excluded. Examples of such conditions can be found in the tables "Causes of Secondary Immunodeficiency" and "Some Drugs that Cause Immunosuppression" in the "Merck Manual"
- Pregnancy, or while breast feeding. Women should not be enrolled within 6 months of giving birth and within 3 months of cessation of breast feeding
- A Body Mass Index > 35
- Cigarette smoker or former smoker who has smoked within 6 months of the start of the study
- Living at an altitude that is more than 1,000 feet (lower or higher) from the study site (which is 4,500 feet above sea level)

- History of:
 - Major depression with psychotic or melancholic features before the diagnosis of ME/CFS, or active depression (major depression with psychotic or melancholic features) as determined by self-report
 - Untreated endocrine diagnoses including hypothyroidism (Hashimoto's, etc.), Grave's disease, adrenal insufficiency, hypogonadism (testosterone deficiency), diabetes mellitus or insipidus
 - Acute infection within the past 30 days
 - Within the last 3 years, any significant head injury, e.g., concussion with loss of consciousness, brain surgery, an automobile accident with head/neck injury, other traumatic brain injury
 - A supra-ventricular tachycardia or ventricular tachycardia, e.g., atrial fibrillation or flutter, paroxysmal atrial fibrillation, junctional tachycardia, ventricular tachycardia
 - Severe baseline hypotension defined as rested sitting systolic BP < 100 mmHg or rested sitting diastolic BP < 60 mmHg. Severe baseline tachycardia (HR > 100 bpm) or bradycardia (\leq 45 bpm).
 - Renal impairment based upon the local lab normal estimated glomerular filtration rate (eGFR) (drug is cleared by passive renal filtration)

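### The pre-infusion start limits for blood pressure and heart rate are nominally looser than the entry limits, so a patient who has drifted outside the entry range by Day 29 may still be infused.

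*Combined protocol and SAP*

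**What the plan says.** Section 1.3.2.2 (Exclusion Criteria) excludes "Severe baseline hypotension defined as rested sitting systolic BP < 100 mmHg or rested sitting diastolic BP < 60 mmHg". It also excludes a heart rate above 100 BPM, or at or below 45 BPM. Section 1.3.3.2.1 confirms eligibility at Visit 1 (Day 1), where vital signs include blood pressure taken twice after 5 minutes sitting.

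Infusions are planned for Days 29, 31 and 33. Section 1.3.1.6 (Dose Discontinuation) lists the values at which a running infusion is stopped. For systolic pressure: "a systolic BP ≤ 90 mmHg or a ≥ 20 mmHg decrease from baseline on 3 consecutive readings". For diastolic pressure: ≤ 50 mmHg, or a fall of at least 15 mmHg, in the same form. For heart rate: "a resting HR ≥ 120 BPM or ≤ 45 BPM". The section then uses the same values as a start gate, applied to the average of two semi-recumbent readings. If that baseline meets them, "at baseline, the infusion must not be administered".

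After a failed gate, the investigator discusses reassessment with the medical monitor: "The time window for reassessment should not be greater than 14 days". The final consequence is stated for the first infusion: "If, after reassessment, the patient does not receive the Visit 3 infusion, then the patient should be discontinued from the study".

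Sections 1.3.3.2.3 to 1.3.3.2.5 (Visits 3, 4 and 4b) call for vitals and the semi-recumbent baseline. They do not re-apply the entry limits.

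**The concern.** A stopping limit marks where a running infusion has gone too far. A start limit should leave room before that point. Using one set of numbers for both allows an infusion to begin one unit from the stop.

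The protocol makes this margin important. Section 1.2.1 names raised heart rate and lowered blood pressure as the principal risks. Section 1.3.1.5 reports that in the first five ME/CFS patients these effects appeared at substantially lower plasma concentrations than in healthy subjects. Section 1.3.1.6 says it is impossible to know the extent of any CRF₂ up-regulation and the "related left-shift of the hemodynamic dose-response curve in ME/CFS patients". Section 1.3.1.5.1 closes the Low dose after clinically significant hemodynamic adverse events.

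Two things are at stake: the safety margin of a patient whose state has changed since Visit 1, and the clarity of the tolerability data. A stop after a small change in a patient who started near the limit is hard to interpret, and a dose group may hold as few as three patients (section 1.3.1.4.2).

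**Working it through.** The plan has no figure of its own to reproduce here. The check sets the two lists of limits side by side.

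**Inputs**

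| Measure | Entry: exclude (1.3.2.2) | Start gate: do not infuse (1.3.1.6) | Fails entry, passes gate |
|---|---|---|---|
| Systolic, mmHg | < 100 | ≤ 90 | 91-99 |
| Diastolic, mmHg | < 60 | ≤ 50 | 51-59 |
| Heart rate, high, BPM | > 100 | ≥ 120 | 101-119 |
| Heart rate, low, BPM | ≤ 45 | ≤ 45 | none |

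The reverse comparison is empty: no whole-number value is blocked by the gate but allowed at entry. A fall from baseline cannot apply at baseline, so only the absolute values work as start limits. The wording about three consecutive readings does not fit a baseline averaged from two. I take the absolute values to apply to that average, the reading under which the blood pressure gate works.

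**Headroom to the absolute stop**

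- At the entry limit: 100 − 90 = 10 mmHg systolic; 60 − 50 = 10 mmHg diastolic; 120 − 100 = 20 BPM.
- In the gap: 91 − 90 = 1 to 99 − 90 = 9 mmHg systolic; 51 − 50 = 1 to 59 − 50 = 9 mmHg diastolic; 120 − 119 = 1 to 120 − 101 = 19 BPM.
- The relative stops lie beyond the absolute ones here. A 20 mmHg fall from 91-99 gives 71-79, already below 90. A 15 mmHg fall from 51-59 gives 36-44, already below 50.

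**Time since the entry check:** 29 − 1 = 28, 31 − 1 = 30 and 33 − 1 = 32 days.

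**Dose context (Table 6.1):** the D2 rate is 0.10 µg/kg/h against 0.20-0.24 for the closed Low dose, so 0.10/0.24 = 42% to 0.10/0.20 = 50%. The total is 0.35/0.80 = 44%.

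**What a sitting entry check would cost through noise.** The documents give no reading variability, so this part is assumed: SD 4-8 mmHg per reading, correlation ρ of 0-0.5 between the two readings, normal errors. The average of two readings has SD × √((1 + ρ)/2). For a patient whose true sitting systolic is 105, the chance that the average falls below 100 is Φ(−5 / SD of the average).

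- SD 4, ρ = 0: SD of the average 2.83; Φ(−1.77) = 3.9%.
- SD 8, ρ = 0.5: SD of the average 6.93; Φ(−0.72) = 23.5%.

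At a true value of exactly 100, about half of checks fail.

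**The case against.** The strongest reply is that the two limits serve different purposes. The entry limits appear in a list headed as history and refer to a rested sitting reading, so they screen for a standing condition. The gate is an acute check in another posture. This stands in part. A reader might infer that the protocol itself classes a patient reading 95 semi-recumbent on Day 29 as severely hypotensive. It does not: that label belongs to the sitting entry measurement. What remains is that nothing numeric carries the entry requirement forward to the day of exposure.

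A reader might also infer that the reassessment route cannot be used at Visits 4 and 4b, because section 1.3.3.1 requires the infusion visits to be 48 to 96 hours apart. The text does not support that. Only the discontinuation sentence names Visit 3, and 14 days is an upper bound, so a recheck inside 96 hours complies. What is missing is the consequence of a second failure there, which is a detail.

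Protections exist. Readings are taken every 15 minutes during the infusion and for at least 90 minutes afterwards, and the absolute stop acts early in a patient who starts near it. The PI may withdraw a patient at discretion (section 1.3.2.3). D1 concentrations stayed below the level at which hemodynamic changes were seen, and section 1.3.1.6 does not expect clinically important changes at the revised doses. All of this lowers the risk. However, the stops act only after exposure has begun, and no value triggers the PI's discretion.

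The looser limits may also be deliberate. Part of the dose justification is redacted, and the section cited for the first five patients (6.1.2.6) and Table 6.2 are not in the text available here.

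**Conclusion.** The point holds as an inexpensive safety improvement. On the visible text, systolic 91-99, diastolic 51-59 and heart rate 101-119 BPM fail entry but permit an infusion to start, with 1-9 mmHg or 1-19 BPM to the absolute stop. A patient at the entry limit has 10 mmHg or 20 BPM. The low heart-rate limit has no gap.

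The size is nominal because the postures differ, and the documents do not say how many patients would drift this far in four weeks. No claim is made that harm is likely.

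A reader might infer that patients starting in the gap will often be stopped by chance. That does not follow. It requires a sustained shift in the true value, for example to a true resting rate near 110. With an assumed SD of 4-8 BPM, correlation of 0-0.5, 14 readings per infusion (210/15) and no drug effect, a patient whose true rate is still 100 but who reads above 100 at baseline meets the heart-rate stop in about 0-8% of infusions. That is the same as for any patient at 100. Nor would one such stop block D2 by itself, since escalation turns on clinically important changes.

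**What to change.** 1. **Visit 3.** Before the semi-recumbent baseline, take heart rate and blood pressure twice after 5 minutes sitting, as at Visit 1, and average them. Do not infuse if the average is systolic < 100, diastolic < 60, heart rate > 100 or heart rate ≤ 45. Then use the existing medical-monitor discussion and reassessment within 14 days.
2. **Keep the existing rules.** The semi-recumbent start gate and the in-infusion stopping rules stay unchanged, as additional protection. State that the start gate applies to the average of the two readings.
3. **Visits 4 and 4b.** Make the same sitting check. If it fails, recheck inside the 48-96 hour window. With visits planned 48 hours apart, the slack is up to 96 − 48 = 48 hours. Leave the decision to dose or omit to the PI and medical monitor. Mandatory omission is not proposed, because it would trade exposure for safety in a small trial.
4. If the looser limits are intended, state the reason in section 1.3.1.6.

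**Cost.** About 5-10 minutes at each of three visits and a few sentences of text. Some patients will be deferred. Under the existing rule, one still not infused at Visit 3 after reassessment is discontinued. A replacement (section 1.3.2.3) must repeat the four-week pre-treatment period. Some failures will be measurement noise: about 4-24% of checks at a true sitting systolic of 105 under the assumptions above, and more nearer 100. The added sitting check does not exclude a patient who passes it but reads, say, 95 semi-recumbent; for that patient the existing gate, monitoring and stopping rules remain the protection.

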1.3.2. Selection of Study Population

1.3.2.1. Inclusion Criteria

Patients who meet all of the following criteria are eligible to participate in the study:

- Provision of signed and dated informed consent form
- Ability to read, understand and speak English
- Living at an altitude between 3,500 and 5,500 feet above sea level for the past 1 year
- Willing to perform an exercise test
- Diagnosed with ME/CFS and meet the following 3 case definitions: Fukuda Research Case Definition for CFS (1994), Revised Canadian Consensus Criteria for ME/CFS (2010) and the IOM Clinical Diagnostic Criteria for ME/CFS (2015)
- Relatively stable state of illness for the individual patient over the past 3 months
- Male or female, between the ages of 18 and 60 years old
- Males or females of reproductive potential agree to remain abstinent or use (or have their partner use) 2 acceptable methods of contraception, starting from the time of informed consent through 28 days after the last dose of study drug. Acceptable methods of birth control during the study are intrauterine device, diaphragm with spermicide, contraceptive sponge, condom or vasectomy. Oral contraceptive pills may not be used as the sole method of contraception because the effect of CT38 on the efficacy of oral contraceptive pills has not yet been established
- Stated willingness to comply with all study procedures and remain available for the study duration
- Have mobile (smart) phone and access to the internet

A patient may be enrolled only once and may only receive the prescribed 2 days of study treatment once.

1.3.2.2. Exclusion Criteria

A patient who meets any of the following criteria will be excluded from participation in this study:

- Alternate medical or psychiatric illness that could explain the ME/CFS symptoms
- Active or uncontrolled co-morbidities which in the opinion of the PI may interfere with the ability of the patient to participate in the study. Co-morbidities may include acute infection, Crohn's disease, diabetes mellitus (Type 1 or Type 2, evidenced by a history of hemoglobin A1C > 7 at any time), Guillain-Barre syndrome, lupus, multiple sclerosis, myasthenia gravis, rheumatoid arthritis, or other such diseases that may be exclusionary. Particularly conditions or medications that cause immunodeficiency or immunosuppression will be excluded. Examples of such conditions can be found in the tables "Causes of Secondary Immunodeficiency" and "Some Drugs that Cause Immunosuppression" in the "Merck Manual"
- Pregnancy, or while breast feeding. Women should not be enrolled within 6 months of giving birth and within 3 months of cessation of breast feeding
- A Body Mass Index > 35
- Cigarette smoker or former smoker who has smoked within 6 months of the start of the study
- Living at an altitude that is more than 1,000 feet (lower or higher) from the study site (which is 4,500 feet above sea level)

- History of:
 - Major depression with psychotic or melancholic features before the diagnosis of ME/CFS, or active depression (major depression with psychotic or melancholic features) as determined by self-report
 - Untreated endocrine diagnoses including hypothyroidism (Hashimoto's, etc.), Grave's disease, adrenal insufficiency, hypogonadism (testosterone deficiency), diabetes mellitus or insipidus
 - Acute infection within the past 30 days
 - Within the last 3 years, any significant head injury, e.g., concussion with loss of consciousness, brain surgery, an automobile accident with head/neck injury, other traumatic brain injury
 - A supra-ventricular tachycardia or ventricular tachycardia, e.g., atrial fibrillation or flutter, paroxysmal atrial fibrillation, junctional tachycardia, ventricular tachycardia
 - Severe baseline hypotension defined as rested sitting systolic BP < 100 mmHg or rested sitting diastolic BP < 60 mmHg. Severe baseline tachycardia (HR > 100 bpm) or bradycardia (\leq 45 bpm).
 - Renal impairment based upon the local lab normal estimated glomerular filtration rate (eGFR) (drug is cleared by passive renal filtration)
 - Known hypersensitivity or clinically significant allergies to... **[proprietary data redacted]** (both excipients in the drug product)
 - Substance abuse in the past 12 months as determined by self-report
- Improvement in overall ME/CFS symptoms as a result of any treatment intervention in the past 3 months
- Current treatment with medications that interact with pathways involving: (i) 5HT (e.g., selective 5HT re-uptake inhibitors or SSRIs, 5HT and norepinephrine re-uptake inhibitors or SNRIs, tricyclic antidepressants, monoamine oxidase inhibitors, triptans); (ii) norepinephrine (e.g., adrenergic agonists or antagonists, norepinephrine re-uptake inhibitors, norepinephrine and dopamine re-uptake inhibitors); (iii) dopamine (e.g., norepinephrine and dopamine re-uptake inhibitors); and (iv) cortisol (e.g., oral glucocorticoids, fludrocortisone). Prior withdrawal of medications, see Section 6.3.4.7.
- Prior treatment with
 - Short-term (< 2 weeks) antiviral or antibiotic medication or flu shot within the past 4 weeks
 - Long-term (> 2 weeks) antiretrovirals within the past 12 months
 - RituximabTM within 6 months
 - Any new prescription drug or herbal remedy within 2 weeks prior to the onset of the trial
- Current participation in another clinical treatment trial

